- 3. Incidence of clinical malaria (definition 1, see section 2.2.2.3) for 12, 24 and 52 weeks after administration of L9LS or placebo.
- 4. Incidence of clinical malaria (definition 2, see section 2.2.2.3) for 12, 24 and 52 weeks after administration of L9LS or placebo.
- 5. Measurement of L9LS in sera of recipients (parts 1 and 2).
- 6. PK analysis of L9LS and the association of L9LS concentration with Pf infection risk.

Part 2 Extension Primary Endpoints:

- 1. Incidence and severity of local and systemic AEs occurring within 7 days after the administration of L9LS and incidence of serious adverse events (SAEs) throughout the study period.
- 2. Measurement of L9LS in sera of recipients.
- 3. Measurement of ADA in sera of recipients.

Part 2 Extension Exploratory Endpoints:

- 1. Pf blood-stage infection as detected by microscopic examination of thick blood smears obtained between 1 week and 52 weeks after administration of a third dose of L9LS or placebo.
- 2. Pf blood-stage infection as detected by RT-PCR from dried blood spots obtained between 1 week and 52 weeks after administration of a third dose of L9LS or placebo.
- 3. Incidence of clinical malaria (see section 2.2.2.3) between 1 week and 52 weeks after administration of a third dose of L9LS or placebo.
- 4. PK analysis of L9LS and the association of L9LS concentration with Pf infection risk.
- 5. PK analysis of L9LS and the association of L9LS concentration with clinical malaria risk.
- 6. Levels of naturally occurring antimalarial antibodies in participant blood at selected time points

Study Population:

We will enroll a total of 396 healthy Kenyan children, including 72 ages 5 months to 10 years residing in western Kenya for part 1 and 324 ages 5-59 months for part 2. The year 2 follow-on study will enroll an additional 24 children into an initial safety study (part 1b) and then participants who are currently enrolled in part 2 of the study and agree to continue in the extension phase will be followed for an additional year.

Phase:

2

Description of Sites/Facilities Enrolling Participants: Study activities will take place at the KEMRI clinical trials unit based in the Siaya County Referral Hospital, which is the largest hospital in Siaya County, western Kenya. In part 2 and the extension phase, study activities will also take place at Kogelo Dispensary, located approximately 12 km from Siaya County Referral Hospital.

Version 6.0 Date: 2 Apr 2024

Description of Study Intervention:

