This will be a phase 2, double-blind, randomized, controlled clinical trial to evaluate the efficacy of L9LS against malaria infection among children ages 5 to 59 months in a setting of perennial high transmission. Participants will be stratified by age group (5-17 months and 18-59 months) and within each age group randomly assigned in a 2:1 ratio to receive L9LS or placebo as an initial injection. The two age groups will be enrolled in parallel. Study arms are as follows:

- 1. L9LS at 10-20 mg/kg (SC administration):
 - a. 5-17 months of age
 - i. L9LS dose 2 at 6 months
 - ii. Placebo dose 2 at 6 months

- b. 18 months to 59 months of age
 - i. L9LS dose 2 at 6 months
 - ii. Placebo dose 2 at 6 months

2. Placebo arm:

- a. 5-17 months of age (with placebo dose 2 at 6 months)
- b. 18 months to 5 years of age (with placebo dose 2 at 6 months)

After an initial screening, we will obtain informed consent from those eligible; for those consenting, we will conduct a more complete screening that includes a physical exam and blood draw to assess parasitemia, hematological and biochemistry values, antimalarial antibody and antigen titers, and other parameters; for those who remain eligible, we will administer a full, weight-based course of DP, the second-line antimalarial in Kenya, to clear parasites. (For children who have taken an antimalarial within the last 2–4 weeks, this antimalarial course will be deferred at least 7 days from the date of the last dose of AL or at least 4 weeks after the last dose of DP.) Between 14 and 21 days after the first dose of DP (considered day 1 for dosing window), children will return and then be randomized to receive a SC injection(s) of either placebo or L9LS, according to study arm. Children will be considered enrolled once they are randomized on the Day 0 dosing visit. We will use a 'constrained' fixed dosing approach that ensures each child receives a minimum of 10 mg/kg in a relatively simple dosing scheme. See section 6.2.4 for exact dosing information and the number of required injections of two syringe types for various participant weights.

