The CDC has collaborated with KEMRI in western Kenya to evaluate tools for malaria transmission and burden reduction for over 40 years. The collaboration has a highly experienced clinical trials unit that includes two pediatricians, immunologists, medical officers, pharmacists, clinical officers, nurses, quality control and regulatory officers. This group has been involved in phase 2, 3, and 4 trials of RTS,S/AS01 and conducted the largest phase 2 trial of the PfSPZ Vaccine in 5- to 12-month-old infants as well as a number of pharmaceutical clinical trials. The clinical trials unit is based in Siaya County Referral Hospital, the largest hospital in Siaya County, western Kenya. Here, malaria transmission is perennial with seasonal peaks following the long and short rains in June/July and November/December, respectively. Clinical malaria incidence (any parasite density by microscopy in a child who reports fever within the previous 24 hours) among children aged 5 to 17 months was 3.06 cases per year in 2019–2020. In the recent PfSPZ Vaccine trial among infants 5-12 months of age at the time of first vaccination (with a 3-dose series over 5 months), 66.7% of participants in the placebo arm had at least one Pf infection based on microscopy within 6 months after the last dose; in another trial among 5- to 17-month-olds at the time of first vaccination (with a 3-dose series over 3 months), 46.8% had at least one clinical malaria episode (parasitemia >0 parasites/µL and fever/history of fever within 24 hours) within 6 months after the last dose. Currently, the RTS,S/AS01 malaria vaccine is being rolled out by the Kenya Expanded Programme on Immunization in select sub-counties in western Kenya; the RTS,S/AS01 vaccine is not being implemented in Alego-Usonga sub-county (where the clinical research site is located). The current Malaria Vaccine Pilot Evaluation is scheduled to run until May 2023, so the earliest that RTS,S/AS01 vaccinations would be offered in Karemo, where the study site hospital is, would be June 2023. In part 2, staff will also recruit and follow up patients at Kogelo Dispensary, a satellite clinic referring patients to Siaya County Referral Hospital.

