9.2.2 Sample Size Considerations for the Efficacy Study

Table 6 shows initial sample size estimations powered to detect a 70% vaccine efficacy (1 – [proportion infected in L9LS/proportion infection in control]) at 12 months comparing L9LS at 10-20 mg/kg to placebo. Sample size calculations were done assuming the endpoint of any Pf infection will be calculated using a proportional analysis, 80% or 90% power, an alpha of 0.05, and that either 30%, 35%, or 40% of children in the placebo group are infected at 6 months and that 40% or 45% are infected at 12 months. (Time-to-event analyses typically require smaller sample sizes.) The primary endpoint will be at 12 months and will combine both MAb age groups who received two doses of L9LS and compare those subjects to the overall placebo group, i.e., we will assess MAb efficacy among children 5–59 months. However, the trial sample size is based on the secondary endpoint of 12-month MAb efficacy with two doses among the younger age group (5–17 months) versus the 5–17-month-old subjects in the placebo group, as these will require larger sample sizes than the primary endpoint. Factoring in 25% loss to followup over 12 months, and a doubling of the sample size in each intervention arm to allow for comparison of L9LS with a second dose (at 6 months) to placebo and comparison of L9LS without a second dose to placebo would require 108 children in each L9LS group and 54 children in the placebo arm, assuming 35% infected in the placebo group at 6 months.

Abbreviated Title: Anti-malaria MAb in Kenyan children

Version 6.0 Date: 2 Apr 2024

Table 6. Sample size calculations based on secondary 12-month endpoint, to achieve 80% power to detect efficacy of 70% at 6 months and 60% at 12 months, assuming 35% of the control group are infected by 6 months and 45% by 12 months.

| Arm | Assumed proportion infected in control group by 6 mos | mAb Efficacy at 6 months | Power | Number needed at 6 months | | Assumed % infected in control group by 12 mos | mAb Efficacy at 12 months | Number needed at 12 months | Number needed to enroll | Number with 20% LTFU* |
|------------------------------|---|-----------------------------------|----------|---------------------------------|-----|---|------------------------------------|-------------------------------------|-------------------------------|-----------------------|
| mAb 5-17 mos + Dose 2 | 0.30 | 70% | 80% | 50 | 120 | 0.40 | 60% | 52 | 104 | 130 |

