9.5.1 General Approach

In general, descriptive statistics will be tabulated by treatment arm for endpoints of interest. This will include point estimates (mean, geometric mean, median, or proportions) and their respective 95% confidence intervals. Formal comparisons will use standard methods, contingency tables for categorical variables, t-tests for comparing means if data follow a normal distribution or geometric means if data after log transformation follow a normal distribution, or nonparametric analogs for comparing medians. Unless specified in the subsequent sections, comparisons will be two-sided with type I error rate of 0.05.

Missing data will be considered as "missing completely at random" provided the amount of missing data is modest (e.g., <10%). We will examine the "missing completely at random"

assumption if the amount of missing data is more than 10%. If the assumption does not hold, missing data will be handled under the "missing at random" assumption (that is, missingness depends only on observed variables) via methods such as multiple imputation and inverse propensity weighting. To handle the possibility of "missing not at random," a sensitivity analysis will be performed by imputing missing binary observations with the observed proportion in the opposite arm. A secondary sensitivity analysis will be considered by imputing missing binary observations as failures.

Randomization: In the efficacy study, participants will be stratified by age (5-17 months versus 18-59 months) and then each age group will be randomized **2:1** to the L9LS arm and the placebo arm. The total number of participants will be 108 in each arm. In the dose-escalation study, participants in each age group, starting with 5-10 years, followed by 5-59 months, will be recruited and randomized 3:1 to receive L9LS at the dose of 5 mg/kg or placebo; if no safety concerns arise, randomization into the L9LS at the dose of 10 mg/kg or placebo, and finally 20 mg/kg or placebo, ensues in the same manner. To limit the number of dropouts before L9LS administration, randomization and L9LS administration will occur as close in time as possible.

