9.5.4 Efficacy Analyses

The primary efficacy endpoint (efficacy study primary endpoint) is the incidence of malaria infection defined as blood smear—positive Pf infection, starting on Day 7 after MAb/placebo administration, through 52 weeks after administration. The secondary efficacy endpoints are the incidence of malaria infection as determined by RT-PCR and the incidence of clinical malaria, up to 12, 24 weeks and up to 52 weeks, as well as the incidence of malaria infection by blood smear up to 12 and up to 24 weeks. The efficacy analyses will be MITT over participants in the efficacy study.

The primary efficacy analysis will be based on time to the first infection. The survival patterns will be described by Kaplan-Meier curves for each arm and compared by the logrank test across different arms. The protective efficacy of the study product will be estimated by the hazard ratio from the Cox proportional hazards model. These analyses will be carried out by R packages or commands in similar statistical software that account for interval censoring: package "interval" for deriving a nonparametric maximum likelihood estimation based on the Kaplan-Meier survival curve and logrank test, and package "icenReg" for Cox proportional hazards regression. To address the heterogeneity of the study population, a Cox regression with regressors other than the study arm will be additionally performed to account for potential differences among participants. The regressors will include time of enrollment and possibly those covariates that are significantly different between the study product arms and the placebo arm in spite of randomization. The primary analysis will compare all children (both age groups) receiving MAb to placebo. Secondary endpoint analyses will compare the younger children receiving MAb to the younger children in the placebo group and the older children receiving MAb to the older children in the placebo group. Since these are secondary endpoints, no adjustments for multiple comparisons will be made.

The secondary efficacy analysis will be based on the proportion of infection. The proportion of infection will be estimated for each arm and compared across arms based on Kaplan-Meier estimates: the proportion of infection by one minus the Kaplan-Meier estimate in the arm, and the vaccine efficacy by one minus the relative risk of infection with melding method for constructing the melded 95% confidence interval of the vaccine efficacy. 34

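### The primary efficacy test and Cox model leave out the randomisation age strata and the recruiting site, and other covariates are chosen by testing baseline differences

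*Combined protocol and SAP*

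**What the plan says.** **Design.** Section 4.1: "Participants will be stratified by age group (5-17 months and 18-59 months) and within each age group randomly assigned in a 2:1 ratio". Section 9.5.1 repeats the age stratification; neither section names site as a factor. The last paragraph of section 5.2 adds that age stratification will be dropped if children under 12 months are excluded from Part 2.

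**Sites.** The abstract places Part 2 at Siaya County Referral Hospital and adds that "study activities will also take place at Kogelo Dispensary", about 12 km away. The study-site text at the end of section 4.1.1 confirms that this is a recruiting site: "In part 2, staff will also recruit and follow up patients at Kogelo Dispensary, a satellite clinic".

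**Primary analysis.** Section 9.5.4 compares arms by a log-rank test and estimates efficacy from a Cox hazard ratio, both allowing for interval censoring, with the two age groups pooled. No strata and no age or site term are named.

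**Covariates.** A further Cox model, additional to the primary one, is meant to deal with heterogeneity between children: "The regressors will include time of enrollment and possibly those covariates that are significantly different between the study product arms and the placebo arm". Age otherwise appears only in separate secondary comparisons within each age group. Site does not appear in section 9.5.4.

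**Later document.** Section 9.5 promises a detailed analysis plan before unblinding that will supersede the protocol. It does not say how strata or covariates will be handled.

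**The concern.** The analysis does not follow the design: age was important enough to stratify on, yet the primary comparison ignores it. Site balance is left to chance, and the primary analysis has no means of allowing for it.

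The covariate rule does not do what its stated purpose requires. A significance test between randomised arms detects chance imbalance, not whether a factor predicts infection. Age is balanced by stratification, so it will hardly ever be flagged. A strong risk factor with moderate imbalance can also pass unflagged. A factor that is flagged reaches only the additional model, and the wording makes even that optional. Different contrasts (two-dose, one-dose, pooled) and the 24-week analysis could each end up with different covariates.

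At stake are how close the estimated hazard ratio is to the within-stratum effect, a little power, and whether the adjusted result was fixed in advance.

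**Working it through.** **Inputs from the documents.** Section 9.5.1: "comparisons will be two-sided with type I error rate of 0.05". Section 9.2.2: "80% or 90% power, an alpha of 0.05". The Table 6 title gives the effect: "to achieve 80% power to detect efficacy of 70% at 6 months and 60% at 12 months". For the control rates, the same title reads "assuming 35% of the control group are infected by 6 months and 45% by 12 months". So 12-month risks are 0.45 on placebo and 0.45 × 0.40 = 0.18 on L9LS. Section 9.2.2 gives 54 placebo and 108 L9LS children per age group, the latter split between one and two doses; overall that is 108 two-dose versus 108 placebo.

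**Assumptions.** The infection hazard ratio between age groups, the hazard ratio between sites, and the share of children at Kogelo are not given. They are varied below.

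**1. The plan's own figure.** Two proportions, unpooled variance:

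n = (z₀.₉₇₅ + z₀.₈₀)² [p₁(1−p₁) + p₂(1−p₂)] / (p₁−p₂)² = 7.849 × (0.2475 + 0.1476) / 0.27² = 42.5, so 43.

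Then 43/0.8 = 54 and 86/0.8 = 108. Table 6 is reproduced. The calculation uses no covariates, so the sample size is unaffected by what follows.

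**2. Attenuation.** Under a constant hazard the within-stratum hazard ratio is ln(0.82)/ln(0.55) = 0.332. The large-sample limit of the unadjusted Cox hazard ratio was found by mixing four equal age-by-site strata and holding overall placebo risk fixed. The 0.889 column assumes a constant hazard applied to the 66.7% six-month placebo figure from the earlier local trial in section 4.1.1: 1 − 0.333² = 0.889.

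| Hazard ratio for age and for site (each) | Unadjusted HR, placebo risk 0.45 | Efficacy, 1 − HR | Unadjusted HR, placebo risk 0.889 | Efficacy, 1 − HR |
|---|---|---|---|---|
| 1 | 0.332 | 66.8% | 0.332 | 66.8% |
| 1.5 | 0.337 | 66.3% | 0.348 | 65.2% |
| 2 | 0.347 | 65.3% | 0.377 | 62.3% |
| 3 | 0.371 | 62.9% | 0.432 | 56.8% |

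**3. Power.** Simulation of 108 versus 108 children with 20% dropout, half at each site, continuous event times, 4,000 runs per row; log-rank unstratified or stratified by age and site.

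| 12-month risks | HR for age and for site (each) | Unstratified | Stratified |
|---|---|---|---|
| 0.45 vs 0.18 (60%) | 2 | 98.0% | 98.7% |
| 0.45 vs 0.18 (60%) | 3 | 97.5% | 99.1% |
| 0.45 vs 0.225 (50%) | 2 | 91.1% | 92.5% |
| 0.45 vs 0.225 (50%) | 3 | 87.8% | 92.6% |

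At 60% efficacy the empirical standard error of the log hazard ratio was 0.27 to 0.29 unstratified and 0.28 to 0.30 stratified. Under no effect, the one-sided rejection rate was 1.8% to 2.2% unstratified against a nominal 2.5%.

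**4. Chance site imbalance.** Assume 30% of children at Kogelo. The SD of the between-arm difference in that share is √(2 × 0.3 × 0.7/108) = 6.2 points, so differences up to 1.96 × 6.2 = 12.2 points escape a p < 0.05 screen. With 216 versus 108 the limit is 1.96 × √[0.21 × (1/216 + 1/108)] = 10.6 points. With exponential risks calibrated to 45% and 18%, at the 12-point boundary (36% versus 24% or the reverse) a true 60% reads as 57% or 63% if one site has twice the hazard, and 55% or 64% at three times. At a one-SD imbalance it reads as 58.5% or 61.5%, and 57.5% or 62.3%.

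**The case against.** A reader might infer that leaving these factors out adds error or makes the primary test unreliable. The calculations do not support that: the standard error is no larger and false positives do not rise.

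A reader might also call the attenuated hazard ratio biased. It is a valid marginal estimate. The difference from 0.332 reflects non-collapsibility, that is, a marginal rather than a within-stratum quantity.

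A large power loss is tempting too. Simulation at 35% efficacy does show gains from adjustment of 62% to 67%, or 65% to 73% with a stronger site effect. But the plan assumes 60% at 12 months, and Table 8 goes no lower than 50%.

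Nor do the documents establish that the sites differ. They give no infection rate or enrolment share by site, all children must live in one sub-county (section 5.1), and section 5.7.2 speaks only conditionally of Kogelo children coming to Siaya for dosing. The 12-point imbalance is a tail case. The 95% interval around 60% with 86 evaluable per arm is about 34% to 76%, from 1 − 0.40 × exp(±1.96 × 0.259), and already covers chance imbalance.

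Finally, age is balanced by design and analysed separately by group, enrolment time is always in the additional model, and a superseding analysis plan is promised.

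All of this limits the size and stands. It does not defend the selection rule, which is unsuited to its purpose. The separate age-group analyses do not adjust the primary estimate, and nothing commits the later plan to a change.

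**Conclusion.** The point holds as one of prespecification with modest consequences. The primary test and model omit the stratification factor and the recruiting site, and the only route for other covariates is a data-dependent screen that feeds an additional model.

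At the planned 45% versus 18%, with age and site hazard ratios of 2 to 3 each, the hazard ratio is 0.347 to 0.371 instead of 0.332, and stratification adds about 1 to 2 points of power; at 50% efficacy, about 1 to 5. Attenuation is larger if infection is much more common than planned. A chance site imbalance would go uncorrected in the primary estimate.

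These sizes rest on assumed age and site effects, an assumed site share and constant hazards. The simulations used continuous event times, not the planned interval-censored software. Power was computed for two-dose versus placebo, the contrast in section 9.2.2; section 9.5.4 can be read as all L9LS recipients versus placebo.

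**What to change.** In section 9.5.4 and in the superseding analysis plan:

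- Stratify the primary log-rank test by randomisation age group, and by recruiting site as well if numbers per site allow.
- Include age group and recruiting site as prespecified terms in the primary interval-censored Cox model.
- If age stratification is dropped under section 5.2, keep age as a covariate.
- Keep time of enrolment as a fixed covariate, and delete selection by significance of baseline differences.
- Keep the unadjusted estimate as a supporting analysis.
- Use the same terms in the 24-week analysis (section 9.5.8) and the extension efficacy comparisons.

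The cost is two extra model terms, both known at entry, and a headline hazard ratio that is conditional rather than marginal and should be described as such. The sample size does not change. The interval-censored fit with these terms should be tried on blinded or simulated data before lock.

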Based on data from Mali suggesting that doses higher than 20mg/kg are needed to protect for 12 months, we propose to assess the safety of an additional two doses: 30 mg/kg and 40 mg/kg in a similar fashion. This extension of part 1 will include an additional 24 children, and will utilize a similar design to before, with 12 participants in each age-dose group in a 3:1 ratio of L9LS to placebo; all participants will be followed for a total of 3 months. However, given that it appears that the younger children are clearing the product more quickly than older people, we will include only children aged 5-71 months, as these are the ages of the children to be included in the part 2 extension. As before, we will ensure safety out to 7 days before proceeding to dose additional subjects.

Part 2: Efficacy study

A total of 324 children 5-59 months of age will be randomized to receive a 10-20 mg/kg dose of L9LS or placebo by SC administration. There will be two L9LS cohorts, one 5-17 months of age and another 18-59 months of age, which will constitute one L9LS arm. A placebo arm will be composed of children 5–59 months of age. They will be followed over 12 months with monthly blood smear microscopy and polymerase chain reaction (PCR) and twicemonthly symptomatology and care-seeking behavior questionnaires. Dosing will be based on three weight bands; all doses will be administered SC with fixed doses of 75 mg L9LS, 150 mg L9LS, or 225 mg L9LS, resulting in a range of 10-20 mg/kg in a double-blinded fashion. Blood will be drawn to assess antibody titers at baseline, and at three additional time points over 12 months to establish pharmacokinetics (PK). Participants in the L9LS arm will be

randomized 1:1 at baseline to receive either a second L9LS injection or a placebo injection to evaluate the additional efficacy of a second dose administered 6 months after the first dose. (Those in the placebo arm will receive a second injection of placebo.) Participants will be followed for an additional 6 months after the second injection with monthly blood smear microscopy and PCR, and a blood draw at month 11 to assess L9LS PK.

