Safety outcomes will be evaluated within arms to assess the safety of a third and fourth L9LS dose vs. placebo in year 2 (1 vs. 3 and 2 vs. 3). Finally, safety outcomes of L9LS vs. placebo will be evaluated in aggregate (1 + 2 vs. 3).

PK of L9LS will be evaluated throughout the study for those receiving various numbers of L9LS doses. The presence of ADA to L9LS will be assessed in sera of recipients at specific timepoints throughout the study and will be correlated with L9LS PK.

In exploratory analysis, L9LS serum concentration will be correlated with the risk of Pf infection (assessed by blood smear and RT-PCR) and clinical malaria. The protective efficacy of L9LS against *P. falciparum* infection (by blood smear and RT-PCR) and clinical malaria will be assessed by comparing: 1) arm 1 vs. arm 3 (over 12 months); 2) arm 2 vs. arm 3 (over 12 months); arms 1+2 vs. arm 3 (over 6 months); and arm 1 vs. 2 (over 12 months).

Study site

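### The 52-week Kaplan-Meier estimate for the two-dose regimen could also use the one-dose children's first 24 weeks: about 25% less variance for one added censoring rule

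*Combined protocol and SAP*

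**What the plan says.** - **Allocation.** Part 2 randomises 324 children 2:1, so 216 receive L9LS at Day 0 and 108 receive placebo (sections 1.1 and 4.1). Section 1.1 says the L9LS children are "randomized 1:1 at baseline to receive either a second L9LS injection or a placebo injection" six months after the first. That gives 108 two-dose and 108 one-dose children, double-blind, in the same weight bands and on the same visit schedule. The second injection is at Day 168, with a window of ±7 days.
- **Objectives.** Section 1.1 asks for two-dose efficacy over 12 months (primary) and, separately, one-dose efficacy over 12 months (secondary).
- **Who is compared.** Section 9.2.2 says the 12-month endpoint "will combine both MAb age groups who received two doses of L9LS and compare those subjects to the overall placebo group". The trial is sized on the two-dose comparison within 5-17 months. Section 9.5.4, in contrast, says the primary analysis takes all children of both age groups who receive the antibody, and does not mention the number of doses.
- **How.** In section 9.5.4 the primary analysis is the logrank test with a Cox hazard ratio, allowing for interval censoring. The analysis labelled secondary estimates "the proportion of infection by one minus the Kaplan-Meier estimate in the arm", with a melded confidence interval for efficacy.
- **Pooling elsewhere.** For the extension, section 4.1.1 lists "arms 1+2 vs. arm 3 (over 6 months" as a comparison. It keeps the 12-month comparisons separate by arm.

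**The concern.** Until Day 168 the one-dose and two-dose children are one randomised population on one blinded treatment. If a one-dose child is censored at Day 168, the censoring is fixed by a baseline allocation and not by anything that happened to the child. That child's first 24 weeks can therefore enter the two-dose curve without bias, and the reverse holds for the one-dose curve. Under the plan's assumptions, 10.5 of the 18 percentage points of L9LS infections fall in that period. A 52-week estimate built from two-dose children alone uses half of the available information on it. What is at stake is precision, chiefly in the 5-17-month comparison, which the plan sizes for 80% power.

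**Working it through.** **Inputs**
- Error rates: "80% or 90% power, an alpha of 0.05" (section 9.2.2), and "comparisons will be two-sided with type I error rate of 0.05" (section 9.5.1).
- Placebo: "assuming 35% of the control group are infected by 6 months and 45% by 12 months" (Table 6 caption).
- Effect: "to detect efficacy of 70% at 6 months and 60% at 12 months" (same caption). L9LS risk is therefore 0.35 × 0.30 = 0.105 at 6 months and 0.45 × 0.40 = 0.18 at 12 months.
- Loss: 20%, as in the last column of Table 6. The text of 9.2.2 says 25%.

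**The plan's own figure.** The two-proportion formula with unpooled variance gives (1.960 + 0.842)² × (0.45 × 0.55 + 0.18 × 0.82) / 0.27² = 7.849 × 0.3951 / 0.0729 = 42.5, so 43 per group, as in Table 6. Then 2 × 43 / 0.80 = 107.5, so 108 per L9LS age group, and 43 / 0.80 = 53.75, so 54 placebo. The inputs are the plan's.

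**Variance of the two-dose 52-week risk, no loss.** Greenwood's formula without censoring gives Var = S² × (1/S − 1)/n, with S(24) = 0.895 and S(52) = 0.82.
- Before week 24: 1/0.895 − 1 = 0.1173. Whole year: 1/0.82 − 1 = 0.2195. Share before week 24: 0.1173/0.2195 = 53.4%.
- Two-dose children only: 0.6724 × 0.2195/108 = 0.00137, SE 0.0370.
- With 216 children before week 24 and 108 after: 0.6724 × (0.1173/216 + 0.1022/108) = 0.00100, SE 0.0316.
- Reduction: 26.7% in variance and 14.4% in SE. That is equivalent to about 147 two-dose children in place of 108.

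**Log relative risk, 108 per group.** Dividing by 0.18² gives 0.0422 before and 0.0309 after. Placebo adds 0.55/(0.45 × 108) = 0.0113. The total falls from 0.0535 to 0.0422, or 21.1%. The interval narrows by 1 − √(0.0422/0.0535) = 11%.

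**With 20% loss (simulation).** Over 20,000 trials the variance of the risk falls 25.1%, and the mean risk is 0.180 with either estimator (true 0.18). With smears read only every four weeks the fall is 25-26%, and the mean risk stays at 0.178-0.180.

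| | SE of log RR | 95% CI at 60% efficacy | Simulated power |
|---|---|---|---|
| 5-17 months, 54 per group | 0.349 to 0.308 | 21-80% to 27-78% | about 81% to 87% |
| All ages, 108 per group | 0.245 to 0.218 | 35-75% to 39-74% | already about 97% or more |

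The intervals are 1 − 0.4 × exp(±1.96 × SE). In the 54-per-group row, a plain normal approximation gives lower power at both ends: 0.916/0.349 − 1.96 = 0.67, or 75%, and 0.916/0.308 − 1.96 = 1.01, or 84%. The log relative risk is skewed at these counts, so the simulated values are the better guide. The gain is of similar or larger size either way.

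**Sensitivity (no loss, variance of the risk).** The reduction is 26.0% with placebo at 30%/40% and 31.1% at 40%/45%. It is 37.6% if 12-month efficacy is 70%, as the text of 9.2.2 has it, and 20.2% if it is 50% (an assumption).

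**The case against.** - **The plan may discard nobody.** Section 9.5.4 speaks of all children receiving the antibody, and section 4.1 defines a single L9LS arm for part 2. Read literally, one-dose children are in throughout. This stands as a criticism of the wording: the two-dose reading rests on the objectives and on 9.2.2. But pooling all 216 over 52 weeks would mix one-dose and two-dose follow-up after Day 168 and would not estimate two-dose efficacy, so the regimen has to be settled in any case.
- **The extension is not a precedent.** A reader might infer that the plan already accepts this device there. It does not: "arms 1+2 vs. arm 3 (over 6 months" is a plain 6-month comparison, and no 12-month curve borrows from another arm.
- **The primary analysis is not shown to gain.** This stands. All the figures concern the Kaplan-Meier proportion. For a single Cox hazard ratio, extra early follow-up would shift the weight towards the first six months.
- **Censoring at an injection actually received goes wrong** for children who miss it, since they would stay in the other regimen's curve. This stands, and the rule below is worded to avoid it.
- **It departs from analysis by assigned group** (section 9.4). That is correct, which is why it belongs beside the as-randomised result.
- **The gain is modest.** For all ages, Table 8 already gives 97% power at these rates. Section 4.1 reports 66.7% placebo infection within 6 months in an earlier infant trial by the same group. If placebo risk were 55-67% with 60% efficacy (an assumption), the plan's formula with 43 per group gives 92-98% power. The narrower interval would remain, but the power argument would weaken.

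**Conclusion.** The point holds as an inexpensive improvement to the regimen-specific 52-week Kaplan-Meier estimates. Variance of the two-dose risk falls about 25%, the efficacy interval narrows about 11%, and power in the 5-17-month group rises from about 81% to 87%. There is little power to gain for all ages.

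A reader might infer that the planned two-dose comparison is biased or wrong. The documents do not support that: it compares randomised groups and is valid, and only efficiency is lost. Nor do they support carrying the figures over to the logrank/Cox primary analysis.

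The size rests on the Table 6 rates, 20% loss, and censoring that does not depend on outcome. The calculations used Kaplan-Meier with Greenwood variance, not the plan's interval-censored and melded methods. Four-weekly detection left the gain unchanged.

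**What to change.** In section 9.5.4, and in the detailed SAP that section 9.5 promises before unblinding:

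1. For each 52-week regimen-specific Kaplan-Meier/melded estimate (two-dose and one-dose, overall and in each age group), add an analysis that includes all L9LS children from Day 7: 216 overall, 108 per age group. Censor children of the other regimen at their Day 168 visit, before the injection, whether or not the injection is then given. If that visit or injection did not take place, censor at Day 168.
2. Keep the as-randomised 108-versus-108 analysis alongside. Leave the primary logrank/Cox analysis and its single hazard ratio unchanged.
3. State that the resulting one-dose and two-dose estimates share children and are correlated. The exploratory one- versus two-dose comparison should therefore stay on the as-randomised groups.
4. Reconcile 9.2.2 (two-dose children versus placebo) with 9.5.4 (all children receiving the antibody), so that the regimen each 52-week analysis estimates is explicit.

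The cost is a few sentences, one censoring rule and one extra set of estimates. No new data, visits or product are needed.
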